## Background

Minimally invasive thoracic surgery, including Video-Assisted Thoracoscopic Surgery (VATS) and Robotic-Assisted Thoracoscopic Surgery (RATS), has become the standard approach for early-stage lung cancer and is widely adopted in clinical practice. These techniques reduce rib injury and nerve traction, thereby alleviating postoperative pain, shortening hospital stay, and facilitating enhanced recovery after surgery (ERAS). Compared with conventional open thoracotomy, VATS and RATS significantly decrease postoperative complications, inflammatory responses, and drainage duration. However, despite their minimally invasive advantages, patients may still experience varying degrees and types of postoperative pulmonary complications (PPCs). Pulmonary complications, particularly infections, remain a leading cause of prolonged hospitalization and postoperative mortality.

Postoperative pulmonary complications are among the most common adverse events following thoracic surgery, typically occurring within 30 days after the procedure, and encompass a range of new-onset respiratory disorders that may negatively affect patient outcomes. Major PPCs include **pulmonary infection, respiratory failure, pleural effusion, atelectasis, bronchospasm, pneumothorax, aspiration-induced lung injury, pulmonary embolism, bronchopleural fistula, and acute respiratory distress syndrome (ARDS)**. Globally, over 300 million patients undergo surgeries requiring general anesthesia with endotracheal intubation each year, and the reported incidence of PPCs ranges from 8% to 40% due to variable definitions.

With advances in ultrasound technology, regional nerve block techniques have become increasingly applied in thoracic surgery. **Paravertebral block (PVB)** has emerged as a safe and effective analgesic method and is gradually becoming a key anesthetic option for thoracoscopic procedures. Ultrasound-guided PVB improves targeting accuracy, reduces complication rates, and enhances postoperative analgesia quality. Beyond pain control, thoracic PVB contributes to hemodynamic stability, attenuates stress responses, and reduces the incidence of postoperative complications. By avoiding contralateral sympathetic blockade, PVB minimizes hypotension and helps maintain stable intraoperative and postoperative hemodynamics, lowering the risk of adverse events caused by blood pressure fluctuations.

Surgical trauma typically induces a stress response, leading to hormonal changes and inflammatory reactions. PVB effectively reduces nociceptive stimulation, thereby attenuating stress hormone secretion, maintaining internal homeostasis, and promoting postoperative recovery. Adequate analgesia and stable hemodynamics also help decrease complications such as postoperative nausea, vomiting, and urinary retention. Furthermore, pain reduction encourages patients to perform deep breathing, coughing, and early mobilization, which supports lung expansion, facilitates sputum clearance, and lowers the risk of pulmonary infection and atelectasis, ultimately promoting rehabilitation.

Therefore, implementing intraoperative paravertebral block in patients undergoing thoracic surgery is of significant clinical importance for reducing postoperative pain and improving outcomes. Investigating the mechanisms by which PVB prevents postoperative pulmonary complications underscores its value, contributes to safer and more efficient thoracic surgery, mitigates adverse events, and enhances postoperative recovery quality.

## Objective

To evaluate the clinical association between intraoperative paravertebral block (PVB) and the reduction of postoperative complications in patients undergoing thoracic surgery.

## Study Design

This study is an **observational investigation combining both retrospective and prospective components**, targeting patients undergoing thoracic surgery, primarily pulmonary and mediastinal procedures.

**Retrospective component:** Data will be collected from patients across multiple campuses of Tongji Hospital who previously underwent thoracic surgery with intraoperative paravertebral block (PVB). These cases will be retrospectively analyzed to examine the association between PVB and postoperative complication reduction.

**Prospective component:** For patients enrolled prospectively, perioperative biochemical parameters—including **MMP3, neutrophils, leukocytes, procalcitonin (PCT), C-reactive protein**

**(CRP)**, and other relevant regulatory factors—will be measured preoperatively and postoperatively. Postoperative outcomes will be assessed by recording **cough and pain scores**, as well as **time to first flatus and defecation** at 24 and 48 hours after surgery. Additionally, the incidence of postoperative complications will be followed up for **30 days postoperatively**.

**Clinical correlation:** The association between the measured biomarkers and patient outcomes will be systematically evaluated to determine their clinical relevance in predicting prognosis and postoperative recovery.

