## Sample Size Estimation

As this study is an observational investigation, the final sample size will depend on the number of patients ultimately enrolled.

Retrospective component: Data will be collected from patients who underwent thoracoscopic surgery at the Department of Thoracic Surgery, Tongji Hospital, Tongji Medical College, Huazhong University of Science and Technology, between January 2024 and December 2024, with a total of 2,000 cases included.

Prospective component: Based on previous similar studies, the anticipated sample size is approximately 50–100 patients. Sample size calculation will be performed using MedCalc software.

Statistical parameters for sample size calculation: Significance level (Type I error,  $\alpha$ ) = 0.01; Power (1 – Type II error,  $1-\beta$ ) = 0.90; Area under the ROC curve (AUC, AZ) = 0.85; Ratio of negative to positive groups = 0.176.

The calculation results are summarized as follows:

		Significance level (Type I error, $\alpha$ )			
		0.20	0.10	0.05	0.01
Power (1- $\beta$ )	0.20	14+3	20+4	27+5	42+8
	0.10	18+4	25+5	32+6	48+9
	0.05	21+4	29+6	37+7	54+10
	0.01	29+6	38+7	46+9	66+12

Based on calculations performed using MedCalc software, the required total sample size for this study is 57 patients. To account for potential attrition during the study, such as loss to follow-up or incomplete data, an additional 10% of participants will be included. Consequently, for each type of thoracic surgery, 63 patients will be enrolled, resulting in a total of  $63 \times 4 = 252$  patients for the study.

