## **Study Procedures**

### **Retrospective Analysis (January 1, 2024 – December 30, 2024)**

Collect baseline and clinical data from patients who underwent thoracic surgery at Tongji Hospital and its affiliated campuses, including sex, age, occupation, past medical history, symptoms and onset time, complete blood count, liver and kidney function, blood gas analysis, coagulation profile, and postoperative inflammatory markers.

Analyze the association between intraoperative paravertebral block (PVB) and postoperative thoracic complications.

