### **Prospective Analysis (Mar 2025 – May 2028)**

Screen patients meeting the inclusion criteria and immediately collect baseline data, including sex, age, occupation, past medical history, symptoms and onset time, vital signs, MMP3 levels, complete blood count, liver and kidney function, blood gas analysis, coagulation profile, and postoperative inflammatory markers.

Record postoperative outcomes at 24 and 48 hours, including cough and pain scores, time to first flatus and defecation, length of hospital stay, and the incidence of 30-day postoperative complications, including pulmonary infection, respiratory failure, pleural effusion, atelectasis, bronchospasm, pneumothorax, aspiration-induced lung injury, pulmonary embolism, bronchopleural fistula, and acute respiratory distress syndrome (ARDS).

Evaluate the association between PVB and MMP3 levels with postoperative thoracic complications and validate these findings against the results of the retrospective analysis.

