### **Between-group comparisons:**

Quantitative variables: analyzed using repeated measures ANOVA or Mann-Whitney U tests.

Qualitative variables: analyzed using Pearson's  $\chi^2$  test.

Ordinal variables: analyzed using Wilcoxon rank-sum tests.

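### Study Design limits the retrospective cohort to patients who had PVB, other sections do not, and no no-PVB comparator is named

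*Protocol*

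**What the plan says.** The Objective section of the Protocol gives one aim: "To evaluate the clinical association between intraoperative paravertebral block (PVB) and the reduction of postoperative complications in patients undergoing thoracic surgery".

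Three sections define the retrospective component.

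- Study Design takes patients from several campuses "who previously underwent thoracic surgery with intraoperative paravertebral block (PVB). These cases will be retrospectively analyzed to examine the association between PVB" and complication reduction.
- Sample Size Estimation, for January to December 2024: "Data will be collected from patients who underwent thoracoscopic surgery at the Department of Thoracic Surgery", "with a total of 2,000 cases included". It sets no PVB condition and gives no split by PVB status.
- Study Procedures, Retrospective Analysis: "Collect baseline and clinical data from patients who underwent thoracic surgery at Tongji Hospital and its affiliated campuses". It also sets no PVB condition, yet asks for the association of PVB with postoperative thoracic complications.

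The statistical section has a heading "Between-group comparisons" that lists tests by type of variable without saying which groups are compared. The Prospective Analysis section relates PVB and MMP3 to complications and then plans to "validate these findings against the results of the retrospective analysis". The Inclusion Criteria do not mention PVB.

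**The concern.** An association between an exposure and an outcome needs variation in the exposure. Study Design selects on the exposure and then asks for its association with complications among the cases so selected. Followed literally, it yields one complication rate in PVB patients and nothing to compare it with.

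The other two sections could supply unexposed patients, but neither says that it intends to, and record extraction cannot satisfy both definitions: one drops no-PVB patients and the other keeps them. At stake is whether the large component can address the stated objective at all, and whether the prospective findings have a retrospective PVB effect to be validated against.

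**Working it through.** The protocol states no figure for a PVB contrast. Its only calculation, 57 patients for an AUC, concerns the prospective part and does not bear on this point.

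**1. The definitions side by side**

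| Protocol section | Who enters | PVB required? | No-PVB group named? |
|---|---|---|---|
| Study Design | Thoracic surgery patients, several campuses | Yes | No |
| Sample Size Estimation | Thoracoscopic surgery patients, one department, 2024, n = 2,000 | No | No |
| Retrospective Analysis | Thoracic surgery patients, hospital and campuses, 2024 | No | No |
| Inclusion Criteria | VATS or RATS patients | No | No |

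The Exclusion Criteria list anesthesiologists not trained in ultrasound-guided PVB. That does not establish a planned no-PVB group either.

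**2. Estimability under the Study Design wording**

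Let PVB = 1 for each of the 2,000 cases. The exposure variance is 0. A model with an intercept and a PVB indicator has two identical columns, so its design matrix has rank 1, not 2. The no-PVB group has n = 0. No risk difference, odds ratio or hazard ratio for PVB can be estimated, whatever the sample size. This step needs no assumption.

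**3. Weight of the component**

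2,000 / (2,000 + 252) = 0.888, or 89%. Sample Size Estimation also gives the prospective size as about 50 to 100 patients. On that figure the share is 2,000 / 2,100 = 95% to 2,000 / 2,050 = 98%.

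**4. Precision under the unrestricted wording (illustration)**

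Inputs:
- N = 2,000 (Sample Size Estimation).
- No-PVB complication rate p0 of 8% and 40%, the ends of the incidence range in Background. That range is for surgery under intubated general anesthesia worldwide, not for no-PVB VATS/RATS patients. A middle value of 20% is assumed.
- Assumed: relative reduction of 30%, so p1 = 0.7 × p0; two-sided 5% level; PVB shares as shown; no adjustment for confounding.

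With n1 PVB and n0 no-PVB cases and pooled rate p = (n1·p1 + n0·p0)/N:

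power = Φ{[(p0 − p1) − 1.96·√(p(1−p)(1/n1 + 1/n0))] / √(p1(1−p1)/n1 + p0(1−p0)/n0)}

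Worked case, p0 = 0.20 and a 90% share: n1 = 1,800, n0 = 200, p1 = 0.14, p = (252 + 40)/2,000 = 0.146. The standard errors are 0.0263 (pooled) and 0.0294 (unpooled). Power = Φ[(0.06 − 1.96 × 0.0263)/0.0294] = Φ(0.29) = 0.61.

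| No-PVB rate | 50% PVB (n0 = 1,000) | 90% PVB (n0 = 200) | 99% PVB (n0 = 20) | 100% PVB (n0 = 0) |
|---|---|---|---|---|
| 8% | 0.57 | 0.30 | 0.10 | not estimable |
| 20% | 0.95 | 0.61 | 0.15 | not estimable |
| 40% | >0.99 | 0.93 | 0.24 | not estimable |

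Simulation with 200,000 draws per cell agrees to within about 0.02. The largest gap is at the 20% rate and 99% share (0.17 against 0.15), where 20 cases strain the normal approximation.

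At a 20% rate, 80% power holds up to a PVB share of about 82% (0.18 × 2,000 = 360 no-PVB cases). There is a lower limit too: power is about 0.80 at a 20% share, 0.53 at 10% and 0.29 at 5%. At an 8% rate, even an equal split gives only 0.57.

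A smaller assumed effect (relative risk 0.75) gives the same pattern. Across rates of 8% to 40%, power runs from 0.22 to 0.81 with 10% no-PVB cases and from 0.42 to 0.997 with an equal split.

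**The case against.** The strongest reply is that Study Design is simply loosely worded. The section with the period and the number of cases, and the section governing data collection, both describe unrestricted surgical patients. The latter asks for the association of PVB with complications in that set, which implies a yes/no contrast. The Inclusion Criteria do not require PVB either, so unexposed patients can enter the prospective part.

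This may well be the intent, and it is why the point is a contradiction to reconcile rather than proof that no unexposed patients will be collected. It does not remove the conflict: Study Design says in terms whose records to use, and on either reading the comparator is unnamed and the PVB share unstated.

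Three further objections have some force:

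- Naming the groups for each test is often left to a SAP. On its own, silence under the between-group heading would not count. Who is in the cohort and what PVB is compared with are design matters, and a SAP cannot restore patients whom the cohort definition excludes.
- The power figures rest on assumed rates, effect and shares. They do, and the contradiction does not depend on them.
- The plan also has biomarker aims, which need no no-PVB group. Those analyses remain possible among PVB patients alone, but they do not answer the stated objective.

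**Conclusion.** The concern holds. The cohort definitions contradict each other and no comparator is named. If Study Design is followed, the PVB–complication association cannot be estimated in the component that holds 89% of the planned patients (2,000 of 2,252, taking 252 as the prospective size), and the prospective results have no retrospective PVB effect to be checked against. That conclusion follows from the wording alone.

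If the unrestricted wording is followed, the contrast may be well powered or nearly useless, depending on a share that the protocol does not give. Under the assumptions above and a 20% no-PVB rate, unadjusted power is 0.95 at an equal split and about 0.15 with 20 no-PVB cases.

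The objective is not wholly lost, because the prospective part is not restricted to PVB, but it has no named comparator either and was not sized for a PVB contrast. This must be fixed before records are extracted or analyzed.

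**What to change.** 1. Use one definition of the retrospective cohort in Study Design, Sample Size Estimation and Retrospective Analysis: eligible VATS/RATS cases from January to December 2024, with and without intraoperative PVB. Settle in the same edit whether one department or all campuses contribute.
2. Record PVB (yes/no) as the exposure, name no-PVB patients as the comparator, and state under the between-group heading that the comparison is PVB versus no PVB.
3. Count the 2024 cases by PVB status and state the expected number in each group.
4. If either group is too small for a useful contrast, say that the retrospective component is descriptive only, and revise the planned validation in the Prospective Analysis section to match.

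The cost is wording in four places and one count from existing records. That enough no-PVB cases exist is an assumption the sponsor must check. If PVB was nearly universal in 2024, rewording will not supply a comparator and step 4 applies.

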## Participant Selection

### Inclusion Criteria

- Male or female participants aged **18 years or older**;
- Scheduled to undergo **thoracic surgery via Video-Assisted Thoracoscopic Surgery (VATS) or Robotic-Assisted Thoracoscopic Surgery (RATS)**, including **wedge resection, segmentectomy, lobectomy, or mediastinal surgery**;
- **Provision of signed informed consent** prior to study participation.

### Exclusion Criteria

- Patients who refuse to provide informed consent.
- Anesthesiologists who have not received training in ultrasound-guided paravertebral block (PVB-US).
- History of ipsilateral thoracic surgery.
- Conversion to open thoracotomy during the procedure.
- Patients who did not complete the scheduled surgery due to disease progression or medical reasons.

- Patients who are lost to follow-up or refuse postoperative follow-up.

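### Eligibility does not ask whether a patient could have received PVB, so patients with a documented contraindication can enter only the no-PVB side of the planned comparison

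*Protocol*

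**What the plan says.** **Eligibility.** Protocol, Inclusion Criteria, admits adults having "thoracic surgery via Video-Assisted Thoracoscopic Surgery (VATS) or Robotic-Assisted Thoracoscopic Surgery (RATS") and names the operations ("including wedge resection, segmentectomy, lobectomy, or mediastinal surgery"). It requires neither receipt of PVB nor suitability for it. In Exclusion Criteria the nearest clinical item is "History of ipsilateral thoracic surgery". The second bullet reads "Anesthesiologists who have not received training in ultrasound-guided paravertebral block (PVB-US"). No item mentions a contraindication to PVB.

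**Planned comparison.** Study Procedures, Retrospective Analysis: "Analyze the association between intraoperative paravertebral block (PVB) and postoperative thoracic complications". Study Procedures, Prospective Analysis: "Evaluate the association between PVB and MMP3 levels with postoperative thoracic complications". Both need patients with and without PVB. Potential Risks and Risk Mitigation says that the study leaves standard care unchanged, so clinicians decide who is blocked.

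**Retrospective cohort.** Study Design describes patients "who previously underwent thoracic surgery with intraoperative paravertebral block (PVB"). Sample Size Estimation describes a wider group: "Data will be collected from patients who underwent thoracoscopic surgery at the Department of Thoracic Surgery", with 2,000 cases and no PVB condition. The two descriptions disagree on whether unblocked patients are included.

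**Data and models.** Both procedure sections collect past medical history and a coagulation profile. Data Collection and Statistical Analysis names multivariable linear, logistic and Cox models without listing covariates.

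**The concern.** In an observational comparison of a procedure with its absence, each patient should have had some chance of either. Here a patient who cannot be blocked is eligible and has only one possible exposure. Such patients collect in the no-PVB group and have no counterparts in the PVB group. If what rules out the block also goes with a higher risk of pulmonary complications, the no-PVB group has the worse prognosis from the start, and a crude analysis credits the difference to PVB.

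The operator bullet may strengthen this. An anaesthesiologist is not a participant, so the bullet can only work by removing that anaesthesiologist's patients. If those patients mostly go without PVB, their removal shrinks the no-PVB group and raises the share of it that could not be blocked.

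At stake is the study's main objective, the association between PVB and fewer complications. The possible bias runs in the direction that the study hopes to find.

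**Working it through.** The protocol gives no figure on this point. Its sample size calculation is for an AUC and does not bear on it. The arithmetic below is an illustration under **no PVB effect**.

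**Inputs, all assumed**
- c = 5% of patients contraindicated
- r1 = 40% complication risk if contraindicated
- r0 = 20% otherwise (the Background section reports 8% to 40% across definitions)
- u = 80% of the remaining patients receive PVB from trained operators

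**Formulas**
- Contraindicated share of the no-PVB group: s = c / [c + (1 − c)(1 − u)]
- No-PVB risk: s·r1 + (1 − s)·r0
- PVB risk: r0, because every PVB patient could be blocked
- Crude risk ratio (RR) = r0 / no-PVB risk

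**Base case**
- s = 0.05 / (0.05 + 0.95 × 0.20) = 0.05 / 0.24 = 20.8%
- No-PVB risk = 0.208 × 0.40 + 0.792 × 0.20 = 24.2%
- RR = 0.20 / 0.242 = **0.83**; the odds ratio (OR) is 0.78

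**One input changed at a time**

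| Change | s | No-PVB risk | RR |
|---|---|---|---|
| u = 50% | 0.05/0.525 = 9.5% | 21.9% | 0.91 |
| c = 2% | 0.02/0.216 = 9.3% | 21.9% | 0.92 |
| r1 = 30% | 20.8% | 22.1% | 0.91 |
| r1 = r0 = 20% | 20.8% | 20.0% | 1.00 |

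**Wider grid.** With c 2% to 10%, u 50% to 95%, r1 1.5 to 2 times r0, and r0 8% to 40%, the crude OR for trained operators' patients runs from 0.32 to 0.98. The low end needs every input at its extreme, including an 80% complication risk in contraindicated patients.

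**Operator bullet.** Suppose further that half of cases have an untrained operator and that none of those patients is blocked (both assumed). Keeping them as controls gives s = (0.05 + 0.05) / (0.24 + 1.00) = 8.1%, a no-PVB risk of 21.6% and an RR of 0.93, against 0.83 with the bullet applied.

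**Removing contraindicated patients.** Both groups then have 20% risk and the RR is 1.00, with or without the operator bullet.

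**Keeping untrained operators' patients only as controls.** After contraindicated patients are excluded, suppose risk under untrained operators is 24% rather than 20% (assumed). The no-PVB risk is (0.19 × 0.20 + 0.95 × 0.24) / 1.14 = 23.3%, so RR = 0.20 / 0.233 = 0.86 under no effect. Dropping the operator restriction for controls alone would exchange one bias for another.

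**The case against.** **Adjustment could deal with this.** A reader might infer that no adjustment can help because the PVB group holds no contraindicated patients. That goes too far. If contraindication is recorded, its stratum contributes nothing to a stratified PVB estimate, and an indicator in a regression does the same work. In the base case the adjusted RR is 1.00. Past history and coagulation profile are collected, regression models are named, and the covariate list may stand in a statistical analysis plan that is not shown. What remains is that the protocol does not call for contraindication to be identified, and raw laboratory values and history entered as general covariates are not the same as a contraindication stratum.

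**The operator rule has a sound purpose.** It plausibly secures uniform block quality, and it keeps operator training balanced between the groups. This stands, and it is the reason for keeping the restriction. A reader might also infer that the rule discards controls who were unblocked for reasons unrelated to their own risk. The protocol does not say this. Assignment of operators may follow campus or case complexity. The bullet concerns training in the ultrasound-guided technique only, so these patients may have been blocked another way. Trained operators may also omit PVB for non-clinical reasons, and those controls remain.

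**The retrospective cohort may contain only PVB recipients.** On the Study Design wording it does, and then the point does not arise there, although the planned association could not be estimated either.

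**The listed data items omit operator training.** It is tempting to conclude that the rule cannot be applied to the 2024 records. The list also omits PVB status and operation type, so it is evidently not a complete list of fields.

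**Conclusion.** The gap is in the protocol text. Eligibility takes no account of suitability for PVB, while the planned analyses compare patients by PVB under usual care. The direction of bias favours PVB only if contraindicated patients are at higher pulmonary risk; with equal risk there is none.

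The size cannot be derived, because the protocol gives neither PVB uptake, nor the share contraindicated, nor the share with untrained operators. The RR of 0.83 is one assumed scenario, not an estimate, and single milder assumptions bring it to 0.91 to 0.92. The added effect of the operator bullet rests on a further unstated assumption, that untrained operators' patients mostly go without PVB.

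The point holds for the prospective component. It holds for the retrospective one under Sample Size Estimation and Retrospective Analysis, which must be reconciled with Study Design. This is a cheap improvement and does not invalidate the design.

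**What to change.** 1. In both components, restrict the PVB versus no-PVB comparison to patients without a contraindication to PVB documented before surgery. The investigators should define in advance what counts. Past history and coagulation profile are already collected and can support the check.
2. In the prospective component, record the reason whenever PVB is not given. It may not be recoverable later.
3. Keep the operator-training restriction and apply it equally to both groups. Reword it as a patient-level rule (patients whose anaesthesiologist is not trained in ultrasound-guided PVB), and record training status. Including untrained operators' patients should be at most a sensitivity analysis.
4. Reconcile Study Design with Sample Size Estimation and Retrospective Analysis on whether the retrospective cohort includes patients without PVB.

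Cost: protocol wording and one or two fields from the anaesthesia record. A few patients are lost to the comparison, and its results apply to patients in whom PVB was an option.

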### **Descriptive statistics:**

Continuous variables: presented as mean  $\pm$  standard deviation (SD) and confidence intervals (CI); when necessary, minimum, maximum, 25th percentile, median, and 75th percentile will be reported.

Paired continuous variables: differences reported as mean  $\pm$  SD.

Non-parametric data: reported as median and mean ranks.

Categorical variables: presented as frequency distributions and percentages.

Ordinal variables: presented as frequency distributions, percentages, median, and mean ranks.

Binary/qualitative variables: reported as positivity rate, number of positive cases, and total sample size.

**Diagnostic evaluation:** When appropriate, the area under the receiver operating characteristic curve (AUC) will be calculated to assess the predictive value of ultrasound parameters.

**Effect analysis:** Associations and predictive effects will be evaluated using correlation analysis, multivariable linear regression, logistic regression, Cox proportional hazards models, and Kaplan-Meier survival analysis.

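### Loss to, or refusal of, postoperative follow-up is an exclusion criterion, so prospective patients are removed after surgery and PVB exposure, inside the 30-day outcome window

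*Protocol*

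**What the plan says.** The last item under Exclusion Criteria reads "Patients who are lost to follow-up or refuse postoperative follow-up". It is not limited to either component of the study.

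The order of events in the prospective component is set elsewhere in the protocol:

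- **Entry.** Inclusion Criteria take patients who are scheduled for surgery, with consent signed "prior to study participation". The Prospective Analysis section says "Screen patients meeting the inclusion criteria and immediately collect baseline data".
- **Exposure.** PVB is intraoperative (Objective; Study Procedures).
- **Outcomes.** The Prospective Analysis section says "Record postoperative outcomes at 24 and 48 hours, including cough and pain scores". Under Study Design, "the incidence of postoperative complications will be followed up for" 30 days after surgery.

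Sample Size Estimation treats the same kind of patient as attrition among those enrolled: "To account for potential attrition during the study, such as loss to follow-up or incomplete data, an additional 10% of participants will be included". The effect analysis paragraph lists "logistic regression, Cox proportional hazards models, and Kaplan-Meier survival analysis" without tying these methods to a named outcome. No section says that lost patients are kept, censored or imputed.

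**The concern.** An exclusion criterion should be decidable when the patient enters. Loss to follow-up is not: it happens after consent, baseline measurement, surgery and exposure, while the outcome is still accruing. Using it as an exclusion selects the cohort on a post-exposure event that may itself depend on the outcome.

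Three things are at stake:

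- The 30-day complication rate is biased if patients with complications are more, or less, likely to be lost.
- The PVB association, which is the study objective, is biased if that relation differs between PVB and no-PVB patients.
- Data already in hand are discarded: 24 h and 48 h outcomes and in-hospital complications of patients lost later.

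If lost patients are treated as never eligible, a reader of the results may not see that any were removed.

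**Working it through.** **1. The protocol's own figures.** Sample Size Estimation gives 57 per surgery type before attrition (48 + 9). A Hanley-McNeil calculation with AUC 0.85, α 0.01, power 0.90 and ratio 0.176, assuming a null AUC of 0.5 and a two-sided test, gives 49 + 9 = 58, within one patient of 57. The attrition step is 57 × 1.10 = 62.7, rounded to 63, and 63 × 4 = 252. With 10% lost, 63 × 0.90 = 56.7 and 252 × 0.90 = 226.8, so about 25 of 252 patients could be removed and about 227 kept. The numbers are compatible with the exclusion. What differs is the status of these patients: enrolled in one section, ineligible in the other. The 10% protects precision and does nothing about selection.

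**2. Size of a possible bias.** Inputs:

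- Overall loss *L*: 10%, from Sample Size Estimation. That figure also covers incomplete data, so 5% is shown as an assumed alternative.
- True complication risk *p*: 20% in both groups (assumed; Background cites a reported range of 8% to 40%). No true PVB effect.
- *k*: ratio of the loss risk in patients with complications to that in patients without (assumed 0.5, 2 or 3).

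Formulas:

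- Loss risk without a complication: Ln = L / (pk + 1 − p)
- Loss risk with a complication: Le = k × Ln
- Observed rate = p(1 − Le) / (1 − L)
- Odds ratio (OR) if the relation holds in the PVB group only = (1 − Le) / (1 − Ln); if in the no-PVB group only, the reciprocal

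Example with L = 0.10 and k = 2: Ln = 0.10 / (0.40 + 0.80) = 0.083; Le = 0.167; rate = 0.20 × 0.833 / 0.90 = 18.5%; OR = 0.833 / 0.917 = 0.91.

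| L | k | Observed rate (true 20%) | OR, PVB group only (true 1) | OR, no-PVB group only (true 1) |
|---|---|---|---|---|
| 10% | 2 | 18.5% | 0.91 | 1.10 |
| 10% | 3 | 17.5% | 0.85 | 1.18 |
| 10% | 0.5 | 21.0% | 1.06 | 0.94 |
| 5% | 2 | 19.3% | 0.96 | 1.05 |
| 5% | 3 | 18.8% | 0.93 | 1.08 |
| 5% | 0.5 | 20.5% | 1.03 | 0.97 |

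Dependence on *p*, with L = 10%, k = 3 and the PVB group only:

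- p = 8%: Ln = 0.10 / 1.16 = 0.086, Le = 0.259, OR = 0.741 / 0.914 = 0.81.
- p = 40%: Ln = 0.10 / 1.80 = 0.056, Le = 0.167, OR = 0.833 / 0.944 = 0.88.

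If loss is unrelated to complications (k = 1), neither quantity is biased. If Le and Ln are the same in both PVB groups, the rate is biased but the OR is not, because the factors cancel.

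**3. Bounds without a model for loss.** Suppose 252 are enrolled, 25 are lost and 45 events are seen in the 227 kept (assumed count; 45/227 = 19.8%). If no lost patient had a complication, the rate is 45/252 = 17.9%. If all did, it is 70/252 = 27.8%.

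**The case against.** The strongest reply is that the plan is coherent as a complete-case design: enrol 63 per surgery type, expect to lose a few, analyse about 57. On that reading the line is merely under the wrong heading, and missing-data methods belong in an SAP that may exist. It is true that the numbers agree and that methods can sit in an SAP. But the protocol does more than leave a gap: it states that these patients are excluded, and an SAP that kept them would contradict it.

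Other objections, and what stands of them:

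- *Refusal can be declared before surgery.* True, and refusal of that kind is an entry matter that the consent criterion already covers. The point applies to loss and to refusal after surgery.
- *The survival methods are tied to no named outcome.* True. Even so, for any endpoint analysed over the follow-up period, excluding every lost patient leaves nobody to censor for loss.
- *The magnitudes are invented.* They are labelled assumptions. The ORs also presuppose outcome-related loss in one PVB group only, and a prospective no-PVB group, which the objective implies but the protocol does not define. They show what is possible, not what will happen.
- *Other exclusions also depend on events after entry* (conversion to open surgery, uncompleted surgery). True, but this point does not rest on them and takes no position on them.

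**Conclusion.** The concern holds: the criterion is wrong as written for the prospective component. That conclusion rests on the order of events stated in the protocol and needs no numerical assumption. The size and direction of any bias cannot be derived from the protocol. Under the assumptions shown (20% risk, 10% loss, a two- to threefold or halved loss risk in patients with complications), the complication rate shifts by 1.0 to 2.5 percentage points. A null OR moves to between 0.85 and 1.18 if the relation is confined to one PVB group. At 5% loss the ORs stay between 0.93 and 1.08. This is moderate, and it should be corrected because the correction is cheap. No claim is made about the retrospective cohort, for which the Retrospective Analysis section sets no follow-up window.

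**What to change.** Take the line out of the Exclusion Criteria and restate it as a withdrawal and loss-to-follow-up rule for the prospective component:

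- Keep every operated, otherwise eligible patient in the analysis set.
- Count complications observed up to last contact.
- Report the number lost by PVB status.
- Where the Kaplan-Meier and Cox methods already listed are used, censor at last contact. This assumes that loss is unrelated to outcome.
- Because that assumption may fail, add a sensitivity analysis for missing 30-day status beside the complete-case result. Best- and worst-case bounds would do. Multiple imputation from in-hospital data is an alternative, but it helps only as far as those data explain the loss.

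The protocol needs only the reworded rule; the analysis details can go in the SAP. The cost is a wording change and a little more analysis, with no extra patients or visits.
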